### **5.9 Clinical Criteria for Early Trial Termination**

Early trial termination will be the result of the criteria specified below:

- Quality or quantity of data recording is inaccurate or incomplete
- Poor adherence to protocol and regulatory requirements
- Incidence or severity of adverse drug reaction in this or other studies indicates a potential health hazard to subjects
- Plans to modify or discontinue the development of the study drugs. In the event of CheckMate decision to no longer supply study drug, ample notification will be provided so that appropriate adjustments to subject treatment can be made.

### **5.10 Surgical Considerations**

The team members will make every effort to comply with the surgical procedures within the time windows allowed in this study protocol. However, under certain circumstances and as discussed between the sub-investigator(s) and the principal investigator, an alteration in the surgical schedule/timing is allowed. These include (but are not limited to) the following:

- A 4 week window between the baseline biopsy and the first dose of nivolumab is allowed.
- The definitive surgery may be a lymphadenectomy or resection of lymphatic metastases as clinically indicated. The definitive surgery may be divided into more than one surgical procedure, scheduled at different time points as clinically/surgically indicated. Under certain circumstances, the definitive surgery may be done after completion of additional therapy (e.g., after the forth dose of nivolumab) or earlier if nivolumab was discontinued due to adverse events or other reasons. Tissue from any of these surgical procedures may be banked under this protocol following the same protocol procedures for tissue handling and banking. The tissue for banking may be digested, frozen or handled in another alternative method as discussed with the investigator.

- If for some reason, the baseline biopsy or definitive surgery could not be completed due to un-anticipated factors such as patient refusal, this will be documented.

**NOTE:** The surgical guidelines are general and may be followed or modified at the discretion of the expert surgical oncologist on the case as clinically indicated and depending on the specifics of the individual surgical case.

For the baseline biopsy required on this study, patients will undergo a core needle, punch biopsy, open surgical biopsy, or other technique at the discretion of the sub-investigator/investigator. The choice of specific surgical technique will be at the discretion of the surgeon or medical oncologist and actual techniques will be the same as those used as therapeutically or diagnostically indicated to surgically treat or confirm the clinical suspicion of recurrent or metastatic disease in any patient undergoing conventional evaluation and treatment (standard of care) within 21 days (preferred; and up to 4 weeks) prior to entry to the study.

### **5.10.1 Primary Excision or Primary Cutaneous Melanoma**

All patients with initial presentation of melanoma T1-4 will be treated by wide excision of the primary. Definitive surgery will include wide excision of the primary and sentinel lymph node assessment. For patients with known primary cutaneous melanoma lesion and no history of wide local excision of that primary lesion, an adequate wide excision of the primary lesion (minimum margin 1 cm) is recommended. The wide local excision will be done at the time of complete lymphadenectomy. Patients with nodal relapse after an inadequate primary excision will undergo wide excision at the time of complete lymphadenectomy. The recommendation for adequate wide excision is the same for patients enrolled at the time of lymph node recurrence as for those enrolled at the time of initial treatment of the primary. For lesions whose Breslow's thickness is > 1 mm, a 2 cm minimum margin is preferred when anatomically feasible (i.e., for lesions of the trunk and proximal extremities). For subungual melanoma, a distal interphalangeal amputation with histologically negative margins constitutes an adequate wide excision. The specimen shall be excised to include skin and all subcutaneous tissue down to the muscular fascia. Fascia may be included at the discretion of the operating surgeon. Closure of the defect may be via primary closure, split thickness skin graft, or rotation-flap at the discretion of the surgeon.

### **5.10.2 Regional Lymphadenectomy**

**Note:** For patients undergoing sentinel node mapping and lymphoscintigraphic and dye lymphographic identification of regional nodal drainage, the minimum number of nodes may be less than the mandatory minimum numbers of 5/groin, 10/axilla, and 15/cervical node dissection.

All patients should undergo one of the following staging lymphadenectomies, as found surgically applicable by the treating surgical oncologist.

#### **5.10.2.1 Head and neck lesions**

Face, ear and anterior scalp: Modified radical neck or radical neck dissection. Parotidectomy to be included if lymphoscintogram indicates flow to the area.

Submandibular and anterior neck: Modified radical or radical neck dissection.

Posterior scalp, posterior neck and uppermost trunk (areas that drain to posterior cervical triangle): Modified posterior triangle neck dissection with suboccipital nodes.

At all times, the number of

#### **5.10.2.2 Upper extremity**

Axillary node dissection to include at least 10 nodes taken from levels I and II. Level III nodes should be dissected if they are clinically involved. The pectoralis minor muscle may be divided or sacrificed at the surgeon's discretion.

#### **5.10.2.3 Lower extremity**

Superficial inguinal node dissection or deep inguinal node dissection will be performed at the discretion of the surgeon. Inguinal node dissection to include at least 5 nodes.

#### **5.10.3 Lymphadenectomy for Nodal Recurrence**

Regional node recurrences will be treated using the appropriate lymphadenectomy procedure. Whenever possible, diagnosis of regional node recurrence will be made using punch or open biopsy technique (if done as part of a clinically indicated baseline diagnostic procedure) to provide baseline pathologic material needed for evaluation of treatment effect. At the time of the definitive lymphadenectomy, the biopsy site will be included in the operative specimen.

### **6 Trial Flow Chart**

The Investigator/Sub-Investigators are expected to make every reasonable effort to comply with the study calendar. However, if a treatment is missed or a subject's study treatment and/or testing days need to be rescheduled due to the subject's inability to comply with the study calendar (i.e., hospitalizations, business and vacation travel plans, illness, transportation issues, holidays, family emergencies, etc.), a window of  $\pm$  one week is available for rescheduling of study treatment and procedures per the discretion of the Sub- Investigator, and as discussed with the Investigator. For the baseline biopsy, a 4 week window is allowed before the first dose of nivolumab and/or CMP-001.

## 6.1 Study Flow Chart

Procedure/ Assessment	Screening (Day -28 to -1) A	Prime Phase (Weeks 1-7)								Surgery	Boost Phase (Weeks 12- 56)	End of Treatment B	30 Day Follow- Up O	Post- treatment surveil- lance N
		W1 D1	W2 D1	W3 D1	W4 D1	W5 D1	W6 D1	W7 D1	W7 D2					
Visit Windows		+/- 2 days		+/- 5 days		+/- 3 days		+/- 7 days		+/- 7 days		+/- 14 days		
CMP-001 dose number C	N/A	1	2	3	4	5	6	7	N/A	N/A	1-12 (12 doses)			
Nivolumab dose number D	N/A		1		2		3		N/A	N/A	D 1-23 (23 doses – if q2) D 1-12 (12 doses – if q4)			
Tumor Biopsy E	X											X B		
Planned Surgical Evaluation and Resection F	X (evaluation)								X (evaluation)	X (resection)				
Exploratory Biomarker Analyses G		X		X				X			X (every 8 weeks starting with Week 12)			
Informed consent	X													
Eligibility Criteria Assessment	X													
Medical History, Demographics, Cancer History including Prior Cancer Medications	X													
Physical Exam H	X	X	X	X	X	X	X	X		X	X	X	X	
Electrocardiogram (ECG) I	X	X		X				X						
Autoimmune lab panel J	X										X			

HCC 17-169

Clinical laboratory tests (hematology, serum chemistry, other chemistry, urinalysis, coagulation tests and thyroid function) J	X		X		X		X			X		X (CBC, CMP, LDH only)	X (CBC, CMP, LDH only)
Urine Pregnancy Test K	X												
Disease Assessment (CT/MRI) L	X							X		X (every 8 weeks starting with Week 20)			
Stool sampling M	X			X			X			X (every 8 weeks starting with Week 12)			
Dietary history questionnaire N	X			X			X			X (every 8 weeks starting with Week 12)			
Adverse Event Monitoring	Assessed continually from informed consent through EOT + 30 days												
Concomitant Medications	Assessed continually from first CMP-001 dose through EOT + 30 days												
30 Day Follow Up O												X	

**Study Calendar Notes:**

A≤4 weeks prior to first dose; magnetic resonance imaging (MRI)/computed tomography (CT) scans may be performed ≤4 weeks prior to first CMP-001 dose.

- During Screening, MRI brain with contrast (or CT equivalent) should be performed to exclude CNS metastatic disease. CNS imaging need not be repeated on study unless patient is symptomatic.

BEnd-of-treatment (EOT) assessments to be performed within 7 days following removal of subject from CMP-001 treatment. Removal of a subject from CMP-001 treatment is defined as the time in which the Investigator decides to discontinue CMP-001 treatment for a subject.

- Management of patients who develop unacceptable toxicity is defined in **Section 5.6**.
  - Patients who develop unacceptable toxicity deemed related to CMP-001 but not Nivolumab may continue Nivolumab after CMP-001 discontinuation for duration as defined in **Section 5.2.2.4**.
  - Patients who develop unacceptable toxicity deemed related to Nivolumab but not CMP-001 must discontinue both CMP-001 and Nivolumab.
- Patients who progress will undergo an optional biopsy to confirm progression at the time of RECIST v1.1 confirmed progression. This biopsy should be done within 14 days of RECIST v1.1 confirmed progression determination.

CCMP-001 is dosed weekly during the Prime Phase and q4 weekly during the Boost Phase of this study.

- Vital sign monitoring.
  - Weeks 1-3 (Prime Phase): vital signs are to be collected within 15 minutes prior to CMP-001 injection, and at 30 (±15) minute intervals for 4 hours following each of the first three CMP-001 injections.
  - Weeks 4-7 (Prime Phase): vital signs are to be collected within 15 minutes prior to CMP-001 injection, and at 30 (±15) minute intervals for 1 hour following each of the first three CMP-001 injections.
  - Boost Phase (all doses): vital signs are to be collected within 15 minutes prior to CMP-001 injection, and at 30 (±15) minute intervals for 1 hour following each of the first three CMP-001 injections.

DNivolumab dosing schedule is q2 weekly during the Prime Phase and either q2 weekly or q4 weekly during the Boost.

- During the Boost Phase of this study, Nivolumab can be dosed q2 or q4 weekly at the discretion of the treating investigator.
- If Nivolumab is dosed at q2 weeks during Boost phase, the patient will receive 23 doses of Nivolumab (doses 1-23; weeks 12-56).
- If Nivolumab is dosed at q4 weeks during Boost phase, the patient will receive 12 doses of Nivolumab (doses 1-12; weeks 12-56).

ETumor biopsy must be performed prior to commencing CMP-001/nivolumab treatment. Tumor biopsy must be of lesion that is planned for resection. Punch, core (>4 18gauge) and/or surgical biopsies are acceptable.

- If core biopsy is performed, pathology confirmation is required to ensure adequate tissue is obtained.

FAssessment of planned resectability must be made DURING screening. Planned surgery after Prime Phase must be with surgeon who initially made determination of planned resectability.

- Extent of surgery to follow guidelines based on location of involved lymph node as delineated in **Section 5.10**.

GExploratory biomarker blood samples are to be collected at the following times:

- Prior to administration of the 1st, 3rd, and 7th CMP-001 doses (W1D1, W3D1, W7D1) respectively.
- Every 8 weeks prior to administration of nivolumab following surgery starting with Week 12.

HA full physical exam will be conducted at screening, each treatment visit and EOT.

- Screening physical exam may be performed up to 72 hours prior to the Week 1 Day 1 visit. If the full physical exam is performed >72 hours prior to the Week 1 Day 1 (W1D1) visit, then a brief (symptom directed) physical exam must be performed within 72 hours prior to initiation of CMP-001.
- Brief physical exams focused on areas of disease or adverse events are performed at the 1st, 3rd, 5th and 7th CMP-001 doses at W1D1, W3D1, W5D1, W7D1 and at any other time as clinically indicated.
- Both full and brief physical exams should include assessment of ECOG performance status.
- Full physical exams should include height and weight.

IElectrocardiograms (ECGs) should be obtained at Screening and prior to administration of CMP-001 at the 1st, 3rd, and 7th CMP-001 dosing visits (on W1D1, W3D1, and W7D1).

- ECG testing is not required during Boost Phase

JClinical laboratory tests may be performed up to 72 hours prior to administration of CMP-001.

- Laboratory tests to be obtained are delineated in **Table 7.1.5.1-1**.

- Autoimmune lab panel to be collected at Screening and EOT only.

KPregnancy testing should be performed in women of childbearing potential and at Screening only.

- This should be done within 7 days prior to receiving the first dose of study drug).
- Any method (urine pregnancy test; serum  $\beta$ -human chorionic gonadotropin) can be utilized for this purpose.

LCT or MRI scans to assess tumor status will be obtained at Screening (baseline value should be performed  $\leq$ 4 weeks prior to first CMP-001 dose).

- Screening:
  - Scans should be performed  $\leq$ 4 weeks prior to first CMP-001 dose).
- Prime Phase:
  - CT (or PET/CT) scans should be repeated prior to surgery (+/- 2 week window).
- During Boost Phase, CT or MRI scans will be repeated every 8 weeks starting with week 20 (or after 2 doses of CMP-001 administered during the Boost Phase **whichever is sooner**).
  - If Nivolumab is dosed at q2 weeks during Boost phase, 1st restaging scan will occur after 4 doses of nivolumab at Week 20 and be repeated q8 weeks.
  - If Nivolumab is dosed at q4 weeks during Boost phase, 1st restaging scan will occur after 2 doses of nivolumab at Week 20 and be repeated q8 weeks.

MStool sampling will be performed at Screening and at W3D1 and W7D1 during Prime Phase. During Boost Phase, these will be repeated every 8 weeks starting Week 12.

NDietary history questionnaire will be performed concordantly with stool sampling at Screening and at W3D1 and W7D1 during Prime Phase. During Boost Phase, these will be repeated every 4 weeks starting with Week 12. Dietary questionnaire is detailed in **Appendix 1**.

O30 day follow up

- This begins +30 days following completion of Cycle 12 Boost Phase.
- Procedures to be followed during this phase are outlined in **Section 7.1.7.3** and will include a visit, bs (CBC, CMP, LDH, TSH, free T4) and any other studied deemed necessary at the discretion of the treating physicians and according to established Standard of Care.

PPost-treatment surveillance (for patients that have completed treatment or removed due to toxicity):

- This phase begins upon completion of 30 day follow up for patients who have completed treatment or come off study due to toxicity.
- Procedures to be followed during this phase are outlined in **Section 7.1.7.2** and will include imaging (CT or PET/CT), labs (CBC, CMP, LDH, TSH, free T4) and any other studied deemed necessary at the discretion of the treating physicians and according to established Standard of Care.

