#### 5.2.2.6 Observation periods

During the Prime Phase, subjects must be observed for a period of at least four hours following each of the first three CMP-001 injections (W1D1, W2D1, W3D1) for signs and symptoms of reactions to the injection and other adverse events. Beginning with the fourth CMP-001 injection (W4D1) the observation period may be reduced to 1 hour following CMP-001 injection or per the discretion of the Investigator and agreement by Sponsor.

During the Boost Phase, subjects must be observed for a minimum of 1 hour following each CMP-001 injection for signs and symptoms of reactions to the injection and other adverse events. Observation periods longer than 1 hour during the Boost Phase should be based on the adverse event profile of the individual subject and be performed at the discretion of the Investigator.

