#### 5.2.2.7 Management of CMP-001 toxicity

##### CMP-001 Associated Adverse Events

If subjects develop inflammation at the injection site this may be managed using cold compresses and/or acetaminophen or non-steroidal anti-inflammatory agents. If flu-like symptoms (i.e., fever, myalgia, and headache) arise, these may be managed using acetaminophen or non-steroidal anti-inflammatory agents.

[figure not shown]
It is expected that symptoms associated with a large release in cytokines at the time of injection could present 1-4 hours after the injection. These symptoms could include: fever, nausea/vomiting, chills/rigors, and hypotension. Subjects must remain in observation until all of these symptoms have resolved to  $\leq$  Grade 1. Refer to **Table 4.1.4-1** for current CMP-001 safety profile in the ongoing CMP-001-001 clinical study.

Subjects who experience a DLT will have dosing of CMP-001 withheld until the toxicity has returned to  $\leq$  Grade 1. If the Investigator determines that continued treatment with CMP-001 is in the subject's best interest, treatment may resume at a reduced dose of CMP-001. Only one dose reduction is allowed. Subjects who still experience DLTs at Dose Level-1 must come off study.

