#### **7.1.3.4 Vital signs**

The investigator or qualified designee will take vital signs at screening, prior to the administration of each dose of trial treatment and at treatment discontinuation as specified in the Trial Flow Chart (Section 6.1). Vital signs should include temperature, pulse, respiratory rate, weight and blood pressure. Height will be measured at screening only.

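### Calendar note C limits timed post-injection vital signs to the first three CMP-001 injections in bullets meant for weeks 4-7 and for all Boost doses

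*Combined protocol and SAP*

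**What the plan says.** Note C to the flow chart in Section 6.1 has one vital-sign bullet for each of three periods. All three ask for readings shortly before the injection and then at roughly 30-minute intervals afterwards: for 4 hours in weeks 1-3, and for 1 hour in weeks 4-7 and in Boost.

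- The second bullet opens "Weeks 4-7 (Prime Phase): vital signs are to be collected within 15 minutes prior to CMP-001 injection" and the third opens "Boost Phase (all doses): vital signs are to be collected within 15 minutes prior to CMP-001 injection".
- Both then restrict the timed readings with the same words: "for 1 hour following each of the first three CMP-001 injections". The weeks 1-3 bullet carries the same restriction with its 4-hour period.

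Section 5.2.2.6 sets how long patients are observed:

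- In the Prime Phase, at least four hours "following each of the first three CMP-001 injections (W1D1, W2D1, W3D1").
- Then: "Beginning with the fourth CMP-001 injection (W4D1) the observation period may be reduced to 1 hour", or as the investigator decides with sponsor agreement.
- In Boost: "subjects must be observed for a minimum of 1 hour following each CMP-001 injection".

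Section 7.1.3.4 asks for vital signs at screening, "prior to the administration of each dose of trial treatment and at treatment discontinuation". It gives no post-injection schedule.

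**The concern.** The restriction to three injections makes sense in the weeks 1-3 bullet, which contains exactly three. In the weeks 4-7 bullet it selects nothing if the injections are numbered as in Section 5.2.2.6. In the Boost bullet it conflicts with the label, which names every dose. Repetition of the same words in a bullet where they cannot apply as defined suggests that they were copied forward, although the document does not settle this.

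This is an instruction that site staff carry out. Followed to the letter, it drops the fixed temperature and blood-pressure readings after many injections. Section 5.2.2.7 expects fever and hypotension as reactions to the injection. Table 4.1.4-1 reports related fever in 57.1% and related hypotension in 28.6% of patients on the weekly schedule in the earlier CMP-001 study. Section 4.1.4 says the acute reactions typically appear after the third dose, so nothing there suggests that monitoring can stop at that point. Different readings of the note would also give uneven vital-sign data and inconsistent decisions on what counts as a protocol deviation.

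**Working it through.** This is a count, so no sample-size formula applies.

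**Inputs**

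- Prime: CMP-001 weekly in weeks 1-7 (note C; flow chart doses 1-7), so 7 injections: 3 in weeks 1-3 and 4 in weeks 4-7.
- Boost: every 4 weeks over weeks 12-56 (note C; Section 7.1.1). The plan states 12 doses. Check: (56 − 12)/4 + 1 = 12, which agrees.
- Total planned injections per patient: 7 + 12 = 19.
- First three injections: W1D1, W2D1, W3D1 (Section 5.2.2.6).

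**Coverage on the Section 5.2.2.6 definition**

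- Weeks 4-7 holds W4D1 to W7D1, injections 4 to 7. None is among the first three, so coverage is 0 of 4.
- Boost: 0 of 12 if the three are counted across the study, or 3 of 12 if counting restarts in Boost, as the flow chart's dose numbering does. Coverage is therefore at most 3 of 12.

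**Injections with no required timed post-injection vital signs, under each reading**

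| How the first three are counted | Weeks 1-3 | Weeks 4-7 | Boost | Covered | Not covered |
|---|---|---|---|---|---|
| Afresh in each bullet | 3 | 3 | 3 | 9 | 19 − 9 = 10 |
| Afresh in each phase | 3 | 0 | 3 | 6 | 19 − 6 = 13 |
| Once across the study | 3 | 0 | 0 | 3 | 19 − 3 = 16 |
| Ignored; bullet labels followed | 3 | 4 | 12 | 19 | 19 − 19 = 0 |

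**Does another section fill the gap?** Section 7.1.3.4 covers screening, pre-dose and discontinuation only. Section 5.2.2.6 sets observation time for signs and symptoms and specifies no readings. Note C is the only source of timed post-injection readings.

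**After correction.** If both later bullets require readings after each injection, coverage is 4 of 4 in weeks 4-7 and 12 of 12 in Boost, which matches the observation periods in Section 5.2.2.6.

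**The case against.** The best case for the present text has four parts.

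*No other rule is contradicted.* Section 5.2.2.6 governs observation time, not timed vital signs, and its list of three visits sits in parentheses in a sentence about the Prime Phase. A reading that empties the weeks 4-7 bullet is the least natural one, and staff would probably follow the label. This shows that the intent can be guessed. It does not make the words correct: the flow chart also numbers weeks 4-7 as doses 4 to 7, so the definition is not an isolated aside. Counting afresh inside that bullet would drop only the seventh injection, for no stated reason.

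*Boost may be a deliberate taper.* Pre-dose vital signs at all 12 doses with timed readings after the first three Boost doses is coherent, and Boost numbering does restart at 1. This stands as a possibility, and the sponsor must answer it. It does not help weeks 4-7.

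*Other safeguards remain.* Pre-dose vital signs and the observation periods apply throughout, and Section 5.2.2.7 adds: "Subjects must remain in observation until all of these symptoms have resolved to" Grade 1 or lower. Symptomatic patients would in practice be measured. This stands and limits the harm, although from W4D1 the length of observation is itself partly discretionary.

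*The readings have modest value.* Section 5.2.2.7 expects cytokine symptoms 1-4 hours after injection, so readings at about 30 and 60 minutes catch only early onset. This also stands.

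**Conclusion.** The concern holds. As worded, the weeks 4-7 post-injection schedule covers 0 of 4 injections on the Section 5.2.2.6 definition, and the Boost schedule covers at most 3 of 12 despite its label. Across 19 planned injections per patient, the number without required timed readings is 10, 13 or 16 by the method of counting, or 0 if the labels override the words. An operative safety instruction should not allow that range.

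The counts assume that all planned injections are given on schedule. Confidence is high that the wording is faulty. The intended Boost schedule is not known from the document. The gap is confined to the fixed post-injection readings. Efficacy, sample size and the DLT window are unaffected: that window covers W1D1 to W3D1 (Section 8.2), where the note is clear. The correction should be made, but its benefit is modest.

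**What to change.** In note C, change the weeks 4-7 and Boost bullets so that the 1-hour readings follow each CMP-001 injection. Leave the weeks 1-3 bullet as it is.

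The sponsor should confirm the Boost intent. If a taper is wanted there, replace the all-doses label with wording that says so: pre-dose vital signs at every Boost dose, and timed post-injection readings after the first three Boost doses only.

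The cost is one phrase in two bullets. Against the present words, the full correction adds about two readings (30 and 60 minutes) at each of 10 to 16 injections, that is 2 × 10 = 20 to 2 × 16 = 32 readings per patient, within the nominal observation hour and with no added visits. If staff already follow the labels, it adds none.
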